Fenofibrate to prevent Ischemic
Cholangiopathy in Donation after Circulatory
Death liver transplantation (FICsDCD)

NCT05514119

28October2022

The FICsDCD Study

MEGA Award Protocol

Title of the study:	Fenofibrate to prevent Ischemic Cholangiopathy in Donation after Circulatory Death liver transplantation (FICsDCD)
Principal investigator:	[name]
Co-investigator(s):	[name], [name], [name]
Mentor:	[name]
Statistician:	[name]
IRB# or Activity#	22-007122

Abstract

Ischemic cholangiopathy (IC) is an early-onset, progressive bile duct stricturing syndrome occurring in 5-15% of transplanted livers, leading to biliary obstruction and allograft failure in up to 60% of cases. There is no definitive treatment for IC besides re-transplantation. The differential rate of IC drives the global preference for livers donated after brain death, over more abundant livers donated after circulatory death (DCD) that are prone to warm ischemia—the primary precipitant of IC. Any intervention to ameliorate IC will likely improve DCD organ utilization globally, thereby reducing transplant waitlist mortality and morbidity. Toxic bile acids (BA) in stagnant bile cause bile duct injury and stricturing, which may explain why stricturing progresses even after ischemia resolves at transplantation. Peroxisome proliferator-activated receptor (PPAR) agonists (such as the generic oral agent **fenofibrate**) potently down-regulate BA synthesis, promote BA excretion, and are safe and effective in other cholestatic diseases, but are not studied in transplant recipients. We hypothesize that fenofibrate could be safe, effective, cheap, and thus generalizable to impede the IC propagation. **In this prospective pilot study, we aim to evaluate 1) the tolerability and safety, 2) the efficacy of 12 weeks once-daily fenofibrate in reducing IC incidence after DCD liver transplantation, 3) assess the association between serum markers of cholestasis and development of IC.** Tolerability and safety will be assessed as proportions of: drug discontinuation, and new grade 3 or 4 adverse events. Efficacy will be assessed as incidence of cholangiographically-diagnosed IC and incidence of any IC-related complication.

Research Plan

Specific Aims

Specific Aim 1: To assess the tolerability and safety of 12 weeks once-daily fenofibrate (Lofibra) in a LT recipient population

Primary endpoint: Proportion of patients discontinuing fenofibrate due to adverse events

Secondary endpoints:

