- a. Proportion of patients with a new grade 3 or 4 adverse event.
- b. Proportion of patients with acute cellular rejection during fenofibrate treatment
- c. Mean change in calculated glomerular filtration rate (eGFR) from baseline during fenofibrate treatment weeks 4, 8, 12, and at 4 weeks after end of treatment
- d. Proportion of patients with myopathy confirmed by serum creatine kinase elevation at weeks 4, 8, 12, and at 4 weeks after end of treatment

The FICsDCD Study

Specific Aim 2: To assess IC incidence after 12 weeks of once-daily fenofibrate (Lofibra) in DCD LT recipients, compared with a historical, untreated control. Treatment and control populations will have an elevated predicted risk of IC, defined as alkaline phosphatase >2.5x upper limit of normal (ULN) at 21-60 days after LT.

Primary endpoint: IC incidence with 12 weeks fenofibrate versus a historical untreated cohort.

Secondary endpoints:

- a. Incidence of any IC-related complication at 12 weeks of fenofibrate treatment as a composite endpoint: biliary intervention (biliary stricture dilation, endoscopic biliary stent placement, percutaneous biliary drain placement), initiation of antimicrobial therapy for cholangitis or biloma, re-transplant evaluation due to IC, or death attributed to IC.
- b. Rate of alkaline phosphatase improvement to <1.67x ULN after 12 weeks fenofibrate.

Specific Aim 3: To assess the association between serum biomarkers and IC development.

Endpoints: Correlation of serum alkaline phosphatase, gamma glutamyl transferase, bile acids, fibroblast growth factor 19 (FGF19) and 7-alpha-hydroxy-4-cholesten-3-one (7AC4) levels at weeks 0, 4, 8, and 12 of treatment, with development of IC at 12 weeks of treatment.

II. Background and Significance

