Liver allografts donated after circulatory death (DCD) improve access to liver transplantation (LT) by increasing organ supply. Widespread adoption DCD LT however is hindered by the higher risk of ischemic cholangiopathy (IC) in DCD organs, a progressive biliary structuring syndrome observed within weeks-to-months after LT, which increases morbidity, mortality, and cost by demanding frequent cross-sectional imaging, endoscopic and percutaneous biliary intervention, hospitalization, parenteral antimicrobials, and in almost 60% of individuals, re-transplantation due to allograft failure.¹ Elevated alkaline phosphatase (ALP) at 1 and 2 months are validated early signals of impending IC, but lack of preventative interventions relegate LT centers to manage complications reactively when they arise.²

Rates of IC in livers procured after brain death (DBD) range 1-10%, while DCD IC rates range 10-30%.³⁻⁵ DCD IC rates are better at experienced centers, with Mayo Clinic Arizona (MCA) and Mayo Clinic Florida (MCF), two of the largest DCD LT centers in the US—having a rate of 10-12% (N=20-24/year).¹ Despite this, the risk of DCD IC dissuades most LT centers from entertaining DCD organs. Almost 30% of recovered DCD livers are unused, compared to 7.5% of DBD livers, and despite their greater abundance, DCD livers account for just 8.5% of the transplanted livers in the United States.⁶ Effective interventions against IC may therefore increase DCD liver utilization.

The key histologic features of early IC are biliary endothelial ischemic necrosis and consequent impairment of biliary drainage (choleresis).^{3,5} The duration of liver non-perfusion after donor cardiac standstill (warm ischemia) is the most important risk factor for IC that explains the higher rate of IC in DCD versus DBD livers, with warm ischemia >30 minutes being a standard cutoff for rejecting an allograft offer.⁷ However, warm ischemia time does not explain the often inexorable progression of biliary destruction well after arterial perfusion is re-established at transplantation. This suggests other ongoing injury processes in the transplanted liver, intervening on which could mitigate the downstream complications of IC.

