An attractive hypothesis for post-transplant IC progression is the accumulation of bile acids (BA)—hydrophobic molecules with detergent and apoptotic effects on hepatocyte and cholangiocyte lipid membranes—within the biliary tree.^{3,8} The pathologic effects of BA are recognized to the extent that flushing the biliary tree to remove BA is standard at time of organ procurement. The immediate post-transplant period is also marked by low concentrations of bile

The FICsDCD Study

phospholipids which impairs BA micellization, and low concentrations of bicarbonate which impairs bile alkalinization, both of which likely potentiate BA-induced cytotoxicity.³ While the antecedent to IC is impaired choleresis due to bile duct necrosis, it is conceivable that BA stasis propagates injury and/or impairs healing after transplantation. The hypothesized process is therefore a spiral of BA accumulation due to ischemia-induced biliary injury, unopposed BA activity due to lower phospholipid and bicarbonate concentrations, BA-induced cytotoxicity, cytotoxicity-induced biliary injury, and further BA accumulation.

Countering the deleterious effects of BA in IC could draw parallels from the treatment of primary biliary cholangitis (PBC) and primary sclerosing cholangitis (PSC), both of which involve disrupted choleresis and accumulated toxic concentrations of BA. Importantly, unlike PSC and PBC where disease progression is fueled by immune activity, the injury trigger in IC appears to be self-limited; ischemia prior to transplantation. It is reasonable therefore to postulate that pharmacologically reducing BA concentrations in a DCD allograft, beginning soon after transplantation, could impede biliary injury and improve allograft survival.

The peroxisome proliferator-activated receptor (PPAR) agonists bezafibrate and fenofibrate (fibrates), which potently downregulate BA synthesis, activity, and promote choleresis, are promising therapeutics for PBC and PSC.^{9,10} At least 11 prospective trials (including one pivotal trial) in PBC (N=481), and 2 prospective trials in PSC (N=23) have demonstrated their ability to improve ALP, BA, and other disease endpoints over the standard of care.¹¹

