While approved for dyslipidemia and used off-label for pre-LT PBC and PSC, fibrate safety or efficacy have not been studied in any transplant population for any indication. Additionally, despite the likely benefits (including cost of \$5-25/month), the known risk profile of fibrates, including nephrotoxicity, hepatotoxicity, and myotoxicity, require study in LT recipients who are prone to these toxicities from immunosuppressives and/or their baseline clinical state.

In this prospective pilot study, our primary aim is to describe the tolerability and safety of 12 weeks of once-daily fenofibrate in a LT population, with efficacy as a secondary aim, and determining associations of cholestasis and bile acid activity biomarkers with IC as a tertiary aim.

We believe this pilot study to have at least four key implications on current post-LT care or in opening new areas of investigation. First, demonstrating fenofibrate tolerability and safety early after LT is useful context of IC but also because both PBC and PSC have a 20% recurrence rate after LT and fenofibrate may be considered for post-LT prophylaxis (current standard of care is universal lifelong ursodeoxycholic acid after LT for PBC, and observation alone after LT for PSC). Second, if an efficacy signal is demonstrated, we will leverage the existing three-site Mayo Clinic collaboration (together the largest transplant consortium by far) to conduct a randomized controlled trial to more conclusively assess efficacy of fenofibrate in preventing IC. Third, we hope to determine if biomarkers besides ALP—a test confounded by other liver processes—are associated with IC and facilitate early detection. Fourth, data gathered may allow us to investigate a predictive scoring model utilizing donor and patient characteristics and these biomarkers.

The FICsDCD Study

III. Progress Report and Preliminary Studies

As two of the largest DCD LT program in the nation, the MCA and MCF transplant hepatology teams including this study's PI and Co-Is are experienced in diagnosing and managing IC. Our group holds a monthly DCD IC Multidisciplinary Conference to review cases and discuss management. Finally, the MCA LT Program has contributed to seminal peer-reviewed papers on the DCD IC syndrome including the recently proposed IC classification system.¹ At present we are developing a dataset of over 300 DCD LT recipients at our center which will be used to identify the historical controls of this study.

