IV. Research Design and Methods

Study design: A single-arm, open-label, prospective study of 12 weeks of fenofibrate (Lofibra) 160mg once daily in donation after circulatory death liver transplant recipients who have serum alkaline phosphatase $>2.5 \times$ ULN 21-60 days after transplantation, to determine fenofibrate tolerability, safety, and efficacy in preventing the ischemic cholangiopathy.

Treatment cohort: Recipients of DCD liver transplants at MCA or MCF

Historical cohort: DCD liver transplant recipients at MCA or MCF between 1/1/2016-6/1/2021

Diagnosis of IC: We will utilize previously-published diagnostic criteria for IC, defined as the occurrence of non-anastomotic biliary strictures in the absence of hepatic artery compromise¹

Inclusion criteria:

1. Female or male patients who have undergone DCD LT
2. At least one serum ALP level $>2.5 \times$ ULN between post-LT days 21-60 days (inclusive) after LT.

Exclusion criteria:

1. LT performed for primary sclerosing cholangitis or primary biliary cholangitis
2. Hepatic artery compromise (e.g thrombosis, stenosis), evaluated on abdominal doppler ultrasonography or angiography prior to enrollment..
3. Untreated biliary anastomotic (surgical) stricture or bile leak between days 0-60 after LT, evaluated during routine clinic examinations, labs, and abdominal ultrasonography.
4. Baseline GFR <30 ml/min
5. Previously known intolerance or allergy to fenofibrate
6. Other clinically significant comorbid condition, including psychiatric conditions, which in the opinion of the study team, may interfere with patient treatment, safety, assessment, or compliance with the treatment
7. Adults lacking capacity to consent to treatment

Interventions:

1. Consenting eligible patients will receive the fenofibrate formulation *Lofibra*, 160mg or renally-adjusted equivalent daily. Intended treatment duration of 12 weeks.
2. Post-transplant laboratory monitoring will be per standard Institutional protocol, at least weekly, through treatment period. Study laboratory monitoring will be done as below.

Analyses:

Specific Aim1:

- a. Tolerability: Proportion of patients who discontinue fenofibrate due to adverse event.
- b. Safety:
 - Proportion of patients with a new grade 3 or 4 adverse events based on CTCAE 5.0 Scale

The FICsDCD Study

- Proportion of patients with acute cellular rejection during fenofibrate treatment
- Mean change in eGFR from baseline at treatment weeks 4, 8, 12, and post-treatment week 4

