The mechanisms of action of PPAR-alpha agonists like fenofibrate predict a strong likelihood of impeding the dreaded transplant complication of IC, yet has not been studied. We propose the first safety and tolerability analysis of fenofibrate in LT recipients. Additionally, we assess the efficacy in reducing IC incidence in a population at increased risk of IC (based on elevated alkaline phosphatase levels at 3-5 weeks after transplant). We proposed fenofibrate as it is readily available and the cheapest PPAR-alpha formulation, at \$5-25/month. Finally, MCA and MCF, as two of the largest DCD LT centers in the nation, makes us uniquely positioned to perform this study, and our existing IC study collaborations in Minnesota and Florida may allow a future multi-center

The FICsDCD Study

randomized controlled trial to more conclusively assess efficacy. Our proposed pilot study is primarily limited by its sample size, owing to a low anticipated IC accrual rate, and the consequent inability to randomize a prospective control arm.

Study Timeline:

Month	0-2	2-4	4-6	6-8	8-10	10-12	12-14	14-16	16-18
Enrolment	X	X	X	X	X				
Treatment	X	X	X	X	X	X	X		
Develop Historical Cohort								X	
Analysis								X	X

V. Human Subjects

Population: The treatment-arm population is 32 adults with decision making capacity, and enrolled from among the MCA and MCF LT recipient population. The control arm is a historical LT recipient population. The study does not involve fetuses, pregnant women, children, prisoners, institutionalized individuals, or others who are likely to be vulnerable.

Research Materials: We will collect, analyze, and biobank blood for study purposes in 32 participants. Participants will receive telephone contact from study coordinators at least monthly during 3 months of treatment, and 1 month after treatment. We will review the electronic medical record of the 32 participants and 116 historical controls including clinical notes, laboratory, imaging, and pathology results, and procedure reports.

Enrolment strategy: Patients who have undergone DCD LT will be screened for eligibility between days 21-60 days after LT. All consecutive LT recipients meeting criteria will be offered enrollment in the study. The historical control cohort will be identified through the Mayo Clinic electronic medical record.

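### The IC endpoint appears to depend on clinically ordered imaging, and the drug may lower the ALP that could prompt it, so less or later looking could pass for efficacy at week 12

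*Combined protocol and SAP*

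**What the plan says.** - **Endpoint.** The Abstract states: "Efficacy will be assessed as incidence of cholangiographically-diagnosed IC". The Aim 2 primary endpoint in Specific Aims is "IC incidence with 12 weeks fenofibrate versus a historical untreated cohort", with no assessment day. Twelve weeks is attached explicitly to the Aim 2 composite and to Aim 3.
- **Case definition.** Section IV, Diagnosis of IC, has it "defined as the occurrence of non-anastomotic biliary strictures in the absence of hepatic artery compromise". It names no imaging modality, timing, trigger or reader.
- **Imaging.** The Schedule of Events covers consent, examination, history, drug, laboratory tests, result review and tolerability checks. No biliary imaging is scheduled.
- **Source of outcomes.** Section V, Research Materials: "We will review the electronic medical record of the 32 participants and 116 historical controls including clinical notes, laboratory, imaging, and pathology results". Procedure reports are also reviewed.
- **ALP as signal.** Section II: "Elevated alkaline phosphatase (ALP) at 1 and 2 months are validated early signals of impending IC". ALP is in the routine laboratory panel, drawn and reviewed weekly on treatment.
- **ALP as drug target.** Section II says that fibrate trials in PBC and PSC "have demonstrated their ability to improve ALP, BA, and other disease endpoints over the standard of care". Aim 2 has as a secondary endpoint "Rate of alkaline phosphatase improvement to <1.67x ULN after 12 weeks fenofibrate".
- **Design.** Single-arm and open-label, with a historical control and a two-sided Fisher's exact test at 0.05. No blinded reading and no common imaging rule for the two cohorts is described. Study Strengths and Limitations names sample size and the lack of a randomized control, not detection.

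**The concern.** Three features combine. The endpoint exists only where someone has imaged the bile ducts; the plan does not schedule that imaging; and the drug is hoped to lower a laboratory value that the protocol itself treats as a warning of IC. Clinicians who see ALP falling in a patient known to be on fenofibrate may image later or not at all. Historical controls had no drug acting on their ALP.

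Delay alone would be enough. Section II describes IC as emerging over weeks to months. If treatment starts on day 21 to 60, twelve weeks (84 days) ends on day 105 to 144 after transplant, and a case worked up after that could be counted as no IC.

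At stake is the reading of the Aim 2 comparison. Section II says that an efficacy signal would lead to a randomized trial. The Fisher test would credit the whole difference to fenofibrate, whatever part came from unequal looking.

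**Working it through.** **1. The plan's own sample size.** Inputs from Section IV, Analyses: 30% versus 5%, 80% power, two-sided 0.05, 1:4 ratio, 10% dropout.

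- Pooled rate: (0.05 + 4 × 0.30)/5 = 0.25.
- Uncorrected n = [1.96 × √(1.25 × 0.25 × 0.75) + 0.842 × √(0.05 × 0.95 + 0.30 × 0.70/4)]² / 0.25² = 23.6, so 24.
- With continuity correction: (23.6/4) × [1 + √(1 + 10/(4 × 23.6 × 0.25))]² = 28.4, so 29 treated.
- Controls: 29 × 4 = 116. Dropout: 29 × 1.1 = 31.9, so 32.

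The stated 32 and 116 are reproduced. Exact Fisher power at 29 and 116 is 87.9%. The sample-size arithmetic is not the problem.

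**2. How few missed cases matter.** With no drug effect and a 30% rate, expect about 35 control cases (116 × 0.30 = 34.8) and about 9 treated cases (29 × 0.30 = 8.7). Against 35/116, Fisher's test gives p = 0.034 for 3/29 and p = 0.10 for 4/29. About six missed or late diagnoses (9 − 3) would therefore produce a significant result.

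**3. Chance of a false signal.** Let the true IC rate be p in both groups, and let a fraction h of treated cases be undetected by the assessment. Observed cases are then Binomial(29, p(1 − h)) and Binomial(116, p). Sum the joint probability over all tables with two-sided Fisher p ≤ 0.05 and a lower treated rate.

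| True IC rate | h = 0 | h = 25% | h = 50% | h = 75% |
|---|---|---|---|---|
| 30% | 1.7% | 8.7% | 31% | 74% |
| 20% | 1.6% | 5.8% | 18% | 49% |
| 12% | 1.2% | 3.1% | 7.6% | 18% |

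The 30% row is the plan's control rate. The 12% row is the top of the two sites' overall DCD rate of 10–12% (Section II); an ALP-selected group may have more. The 20% row lies between. With all 32 treated patients analysed, the 30% row becomes 1.6%, 9.2%, 34% and 79%. The documents give no value for h, so these columns illustrate sensitivity and do not estimate the bias.

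**4. The opposite direction.** If half of the control cases went unseen and none of the treated cases did (30% treated versus 15% control observed), the same enumeration gives about a 40% chance of a significant result against fenofibrate. Unequal looking distorts the test either way.

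**The case against.** A reader might infer that IC is found only when a raised ALP prompts a cholangiogram, that fenofibrate is known to lower ALP in these patients, and that the bias must therefore favour the drug. The documents do not support that chain.

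- No section states what triggers cholangiography. Section II says IC demands frequent cross-sectional imaging, and Section III describes a monthly multidisciplinary IC conference. Imaging outside the study schedule is not excluded.
- The ALP signal cited in Section II is at 1 and 2 months, and both cohorts must have ALP above 2.5x ULN on days 21–60. Every treated patient is already flagged before the drug starts, so a later fall could affect only later imaging decisions.
- The ALP evidence is from PBC and PSC, both excluded here as transplant indications, and Section II states that "fibrate safety or efficacy have not been studied in any transplant population for any indication". The secondary endpoint shows that a fall is hoped for, not that it is established.
- Controls could be missed too, since nothing shows that they were imaged systematically. Section V adds study staff to the transplant programme's monitoring and lists raised liver enzymes (3–13%) on fenofibrate; either could lead to more imaging of treated patients.
- The Aim 2 primary endpoint gives no assessment day, so the delay argument rests on reading it at about week 12.
- Efficacy is a secondary aim of a pilot, and the composite includes antimicrobial treatment, re-transplant evaluation and death, which depend less directly on ALP-led imaging.

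All of this stands as a limit on the size and direction of the bias. It does not remove the ambiguity: the plan collects nothing by design that would show whether the two cohorts were looked at equally.

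**Conclusion.** The point holds as a conditional one. As written, the plan cannot separate a lower IC rate on fenofibrate from less frequent or later imaging, and its stated limitations do not mention this. With no drug effect, the chance of a significant result favouring fenofibrate could rise from 1.2–1.7% to between 3% and 74%, across true rates of 12–30% and hidden fractions of 25–75%. That range rests on assumed hidden fractions, on assessment at about week 12, and on imaging being clinically ordered. The documents establish neither that imaging will be reduced nor which way any imbalance will run. The change is worth making because it is cheap and the result decides whether a randomized trial follows; confidence in a material bias is medium.

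**What to change.** In Specific Aim 2 and its analysis section:

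1. Besides week-12 status, abstract IC status from the record in both cohorts at the same fixed post-transplant day, chosen so that treated patients are off drug. Day 180 would serve if treatment starts by about day 60: 60 + 84 + 28 = day 172. The protocol gives days 21–60 as the screening window and does not state a latest start day, so that assumption should be written down. Describe an efficacy signal only if the difference has the same direction and similar size at both time points.
2. For each cohort, report the number, timing and recorded indication of cholangiograms in the window, and interpret the Fisher result in light of any imbalance.

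An analysis restricted to IC whose imaging was prompted by something other than ALP should not be added. It selects on a variable that the drug may change. If, with no drug effect, half of the control cases were ALP-prompted and no treated cases were, the comparison would be 30% versus 15%, with the 40% chance of spurious harm shown above.

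**Cost.** Wording changes and some extra chart abstraction. Imaging and procedure reports are already to be reviewed for all 32 + 116 = 148 patients, and no procedure or visit is added. Enrolment runs to month 10. A patient enrolled then on day 21 reaches day 180 after a further 159 days, at about month 15 of the 18-month timeline. The downside is that some IC present by day 180 may be unrelated to the treatment window.

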- Proportion of patients with elevated serum CK at weeks 4, 8, 12, and post-treatment week 4

Specific Aim 2:

- a. Efficacy: We will use a two-group design to test whether Group 1 (treatment) proportion (P1) is different from Group 2 (control) proportion (P2) ($H_0: P_1 - P_2 = 0$ versus $H_1: P_1 - P_2 \neq 0$). We will use a two-sided, two-sample Fisher's Exact Test with Type I error rate (α) of 0.05.
- b. Sample size: Allowing a 10% dropout rate, a sample size of 32 in the treatment arm and 116 in the historical control arm (1:4 ratio) will achieve 80% power to detect an IC proportion reduction of 30% in the control arm to 5% in the treatment arm.

Specific Aim 3: Serum biomarker association with IC development: We will use the Wilcoxon Rank-Sum test to compare serum ALP, gamma glutamyl transferase, serum BA, FGF19 and 7AC4 levels at weeks 0, 4, 8, and 12 of treatment, with development of IC at 12 of treatment.

Data management: The study will use REDCap, a secure web platform for building and managing online databases and surveys for electronic data collection. REDCap provides automated export procedures for seamless data downloads to Excel and common statistical packages (SPSS, SAS, Stata, R), as well as a built-in project calendar, a scheduling module, ad hoc reporting tools, branching logic, file uploading, and calculated fields.

Schedule of Events

Procedure	Screening: Post-LT day 21-60	Treatment			Post Treatment
		Weeks 0-4	Weeks 5-8	Weeks 9-12	Week 4
Informed consent	X				
Inclusion and exclusion criteria	X				
Physical examination	X				
Medical history	X				
Intervention: fenofibrate		Daily	Daily	Daily	
Routine Labs*	X	Weekly	Weekly	Weekly	Weekly
Study Labs**	X	Once ^{a,b}	Week 6 ^b	Week 12 ^b	Once ^b
Lab result review		Weekly	Weekly	Weekly	Once
Assess tolerability, safety		Weekly	Once	Once	Once

*Protocol transplant monitoring labs (billed to insurance): total bilirubin, ALP, alanine aminotransferase, aspartate aminotransferase, sodium, potassium, creatinine, eGFR, and complete blood count.

**Study labs per FICsDCD budget: GGT, serum bile acids, CK, FGF19 (ELISA), 7AC4 (LC-MS)

^a collect within 3 days after start of treatment

^b combine with transplant monitoring labs

Study Strengths and Limitations:

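### The source of the historical controls is described as one centre in one section and two centres in another, and the Aim 2 test does nothing to control centre mix

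*Combined protocol and SAP*

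**What the plan says.** All references are to the combined protocol and SAP.

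- **Section III (Progress Report and Preliminary Studies)** says that the team is developing "a dataset of over 300 DCD LT recipients at our center which will be used to identify the historical controls of this study". The sentence just before it is about the MCA liver transplant program.
- **Section IV (Research Design and Methods)** defines the arms as "Treatment cohort: Recipients of DCD liver transplants at MCA or MCF" and "Historical cohort: DCD liver transplant recipients at MCA or MCF between 1/1/2016-6/1/2021".
- **Section V (Human Subjects, Enrolment strategy)** says: "The historical control cohort will be identified through the Mayo Clinic electronic medical record". No site is named.
- **Section IV, Analyses, Specific Aim 2** gives the test: "We will use a two-sided, two-sample Fisher's Exact Test with Type I error rate (α) of 0.05". It states that "a sample size of 32 in the treatment arm and 116 in the historical control arm (1:4 ratio) will achieve 80% power" for a fall in IC from 30% to 5%, allowing 10% dropout.

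No section sets the number of controls or treated patients from each centre, or provides for stratification, matching or adjustment by centre. Study Strengths and Limitations mentions the sample size and the lack of a randomized control arm, but not centre.

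**The concern.** Someone building the control cohort from Section III could take controls from one centre only. Someone building it from Section IV would take them from both. The treated arm comes from both in either case.

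If the two arms have different centre mixes, any difference between centres in IC risk, case mix or the intensity of cholangiographic imaging enters the Aim 2 comparison as an apparent drug effect, and an unstratified test cannot separate the two. Following Section III literally gives the extreme case. Section IV alone does not remove the problem, because it names the eligible centres without fixing the mix of either arm.

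Section II says that an efficacy signal would lead to a randomized trial, so a false or a missed signal has consequences. Centre mix is also one of the few sources of bias in a historical comparison that the sponsor can remove at the design stage.

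**Working it through.** **Inputs from the documents.** IC 30% in controls and 5% in treated, two-sided alpha 0.05, 80% power, 1:4 ratio, 10% dropout, 32 treated and 116 controls (Section IV, Specific Aim 2).

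**Step 1: reproduce the planned size.** With r = 4, the pooled proportion is (0.05 + 4 × 0.30)/5 = 0.25.

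n = [1.960 × √(1.25 × 0.25 × 0.75) + 0.842 × √(0.05 × 0.95 + 0.30 × 0.70/4)]² / 0.25² = (0.949 + 0.266)²/0.0625 = 23.6.

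The continuity correction multiplies this by ¼[1 + √(1 + 2 × 5/(23.6 × 4 × 0.25))]², giving 28.4, so 29 treated and 4 × 29 = 116 controls. Then 29 × 1.1 = 31.9, or 32 treated. The plan's figures reproduce, with dropout applied to the treated arm only. Exact Fisher power at 29 v 116 is 87.9%.

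**Step 2: what an imbalance in centre could do.** The centre rates and the treated split below are assumptions, since the documents give neither. Take an inert drug, all controls from centre A with 30% IC, and half of the treated from centre B with rate b. The treated rate is then 0.5 × 30% + 0.5 × b. I enumerated every pair of outcomes at 29 v 116, marked those with Fisher p ≤ 0.05, and summed their binomial probabilities.

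| Centre B rate | Treated rate | Significant, favouring drug | Significant, either direction |
|---|---|---|---|
| 30% | 30.0% | 1.7% | 4.0% |
| 25% | 27.5% | 3.1% | 4.2% |
| 20% | 25.0% | 5.3% | 5.8% |
| 15% | 22.5% | 8.7% | 8.9% |

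If the treated split is fixed at 15 and 14 patients, the last three figures favouring the drug become 3.0%, 5.0% and 8.0%.

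**Step 3: the opposite direction.** Let the control centre have 20% IC and the other centre 30%, with half of the treated from each. With an inert drug, the chance of a significant benefit falls to 0.4%. With the planned relative risk (5%/30% = 1/6), the treated rate is 25%/6 = 4.2%. Power is 56% against controls at 20%. Against controls with the same centre mix as the treated (25%), it would be 79%. The plan's 88% is not the right comparator here, because it assumes a 30% control rate.

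**Step 4: a centre-stratified exact test with controls from both centres.** I simulated the exact conditional test (60,000 replicates per case) with 15 and 14 treated.

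- Power at 5% v 30% is 88% with controls split 58/58. It is 86 to 87% with controls split 87/29 in either direction.
- With an inert drug and centre rates of 30% and 15%, the chance of a significant benefit is 1.5 to 1.6% under all three splits.

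**Step 5: why both parts of the change are needed.** A centre with no controls contributes nothing to a stratified test. If controls come from one centre only, the comparison rests on that centre's treated patients. With 14 to 16 of them against 116 controls, exact power at 5% v 30% is 51 to 60%.

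**The case against.** The strongest reply is that Section IV is the operative text and already draws both cohorts from the same two centres. Section III is a progress report on a dataset still being built. Its paragraph opens with the MCA and MCF teams together, so the singular may be loose wording. The timeline in Study Strengths and Limitations puts cohort development at months 14 to 16, so nothing is fixed yet. This is fair, and it may mean that one sentence needs correcting. It does not answer the second half of the point: even under Section IV, nothing aligns the centre mix of the arms or accounts for it in the test.

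A second reply is that the centres may differ little. That also stands. Section II gives only a joint figure, "having a rate of 10-12% (N=20-24/year", for all DCD recipients. A small gap does little harm: with centre B at 25%, rejection in either direction is 4.2%, still below 5%. The joint figure does not, however, bound the gap in the high-ALP subset that Aim 2 uses.

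A third reply is that efficacy is a secondary aim of a pilot. This limits the stakes without removing them.

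Three stronger readings are tempting and are not supported:

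- **A reader might infer that the dataset's size shows a one-centre source.** If the annual N means IC cases, 20/0.10 = 24/0.12 = 200 transplants a year. Over 5.42 years that is about 1,083, of which 300 is 28%. But 300 is given as a lower bound, constant volume is assumed, and two centres of similar size would have about 540 each. So 300 fits an unfinished two-centre dataset as well as one centre. Likewise, 300 × 10-12% / 30% = 100-120, close to 116, holds for any 300 recipients wherever they were transplanted.
- **A reader might infer that the writers' centre must be Arizona**, because the plan speaks of "our existing IC study collaborations in Minnesota and Florida". This is suggestive, but does not settle which records will be used.
- **A reader might count the electronic record in Section V as a third, conflicting source.** It is compatible with either of the other two statements.

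**Conclusion.** The point holds as an inconsistency to be reconciled, together with a gap in the analysis. The documents do not establish that controls will come from one centre, or that the result will be biased. They leave that possible and provide no safeguard.

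The size and direction cannot be derived from the documents. Under the assumptions in Step 2, the chance of a false benefit is 3.1 to 8.7% instead of 1.7%. If the control centre has the lower IC rate, the bias runs against the drug. A reader might take the upper figures as the expected error of the trial. They are not: they need all controls from one centre, an equal split of treated patients and a gap of up to 15 percentage points between centres, none of which the documents state. The general DCD range of 10-30% in Section II does not describe a gap between these two sites.

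**What to change.** 1. Amend the sentence in Section III to agree with Section IV: controls are eligible recipients at both MCA and MCF within the stated window.
2. In Specific Aim 2, replace the crude Fisher test with an exact test stratified by centre, such as an exact Cochran-Mantel-Haenszel test.
3. Report IC counts by centre and arm.

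The cost is a change of wording and a record query at the second centre, which Section V already allows. The planned 32 and 116 can stay. The change in power is negligible: about 86 to 88% at 29 v 116 under 5% v 30%, against 88% unstratified. Matching controls to the treated enrolment ratio is not required, since stratification deals with unequal mixes as long as both centres supply controls. Restricting Aim 2 to one centre is not a good substitute, because of the loss of power shown in Step 5.
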